3.4.1.3 End of treatment period procedures

Patients removed from study treatment for reasons other than progression of disease should continue to be followed for first disease progression per RECIST. See footnote #5 in 3.4.1 for details.

All patients who terminate treatment with RAD001 should be evaluated in the outpatient clinic within 5 business days after the last dose of RAD001 and again 4 weeks after their last dose of RAD001 (plus or minus one week depending on appointment availability due to holidays or unforeseen events). In certain instances, if a patient is unable to return to clinic every effort should be made to follow-up with a phone call to the patient or their provider.

This evaluation will include:

Physical examination,

ECOG performance status,

blood pressure, respiratory rate, resting pulse, temperature, and weight.

Patient reported outcomes questionnaire (EQ-5D), see appendix

Medullary thyroid cancer-related symptoms questionnaire, see appendix

Laboratory evaluations are also performed according to table 3.4a. The necessary components of the laboratory tests are outlined below. Documentation of all adverse events

3.4.1.4 Study procedures

3.4.1.4.1 Laboratory evaluations

Hematology

Hematology must include hemoglobin, hematocrit, platelets, total white blood cell count (WBC) and differential. PT (INR) evaluation will be included for baseline evaluations.

ANC will be determined by this equation:

$$(\% \text{Neutrophils} + \% \text{Bands}) (\text{WBC Count} \times 10^1) = \text{ANC}^1$$

Blood chemistry

Blood chemistry must include sodium, potassium, chloride, bicarbonate, calcium, glucose, creatinine, blood urea nitrogen, albumin, total protein, SGOT (AST), SGPT (ALT), total bilirubin, alkaline phosphatase, uric acid, phosphorus, serum lipid profile (triglycerides, total cholesterol, HDL and LDL).

¹ WBC Count is in K/UL units.

Because accurate serum glucose and lipid measurements are required, patients should be fasting at the time of the blood sampling.

Tumor markers which were elevated prior to treatment start with RAD001 will be assessed every month or whenever clinically indicated. Patients with differentiated thyroid cancer will have thyroglobulin and thyroglobulin antibody measured every month and patients with medullary thyroid cancer will have CEA and calcitonin levels evaluated every month (see table 3.4a)

The Hepatitis B and C screening tests (Hep B Core, Hep B Surface antibody, Hep B Surface antigen, HCV RNA-PCR) need to be performed at baseline. HBV DNA follow-up testing should be done according to table 3.4a and section 3.2.6 “Management of Hepatitis B or C Reactivation,” depending on results from baseline.

Urinalysis

Standard urinalysis assessment (pH, protein, glucose, blood, ketones, and leukocytes) should be performed at baseline. This must be supplemented with laboratory quantification of any potentially relevant abnormalities.

Vital signs

Vital sign assessment consists of height (first visit), pulse, blood pressure, respiration rate, temperature and weight. Blood pressure, pulse and respiration rate should be measured on patients after at least 3 minutes in the sitting position.

Physical examination

Physical examination will be performed monthly and must comprise a total body examination. Significant findings made after the start of study drug which meet the definition of an Adverse Event must be recorded.

ECG

A standard 12 lead ECG is to be performed during screening and significant findings must be recorded.

Performance status

Performance status will be assessed according to the ECOG performance status scale at the screening visit and monthly thereafter (see schedule of assessment, appendix B).

Special tests

Special tests may be added in a future amendment.

Drug levels and pharmacokinetic assessments

No drug levels will be assessed.

3.4.2 Efficacy assessments

Progression-free survival will be measured based on the appearance of disease progression on imaging based on RECIST criteria (see Appendix A). This can be on imaging studies that are part of the regular study schedule or based on studies which were obtained based on the appearance of symptoms.

3.4.3 Safety assessments

Safety assessments will consist of monitoring and recording all adverse events and serious adverse events, the regular monitoring of hematology, blood chemistry and urine values, regular measurement of vital signs and the performance of physical examinations.

These assessments should be performed within 1 week of the scheduled day of assessment except for adverse events that will be evaluated continuously through the study. Safety and tolerability will be assessed according to the NIH/NCI CTC <http://ctep.cancer.gov/forms/CTCAEv3.pdf>.

3.4.3.1 Adverse events

Information about all adverse events, whether volunteered by the subject, discovered by investigator questioning, or detected through physical examination, laboratory test or other means, will be collected and recorded and followed as appropriate.

An adverse event is the appearance or worsening of any undesirable sign, symptom, or medical condition occurring after starting the study drug even if the event is not considered to be related to study drug. Medical conditions/diseases present before starting study drug are only considered adverse events if they worsen after starting study drug. Abnormal laboratory values or test results constitute adverse events only if they induce clinical signs or symptoms, are considered clinically significant, or require therapy.

The occurrence of adverse events should be sought by non-directive questioning of the patient at each visit during the study. Adverse events also may be detected when they are volunteered by the patient during or between visits or through physical examination, laboratory test, or other assessments. As far as possible, each adverse event should be evaluated to determine:

- the severity grade (mild, moderate, severe) or (grade 1-4)
- its relationship to the study drug(s) (suspected/not suspected)
- its duration (start and end dates or if continuing at final exam)
- action taken (no action taken; study drug dosage adjusted/temporarily interrupted; study drug permanently discontinued due to this adverse event; concomitant medication taken; non-drug therapy given; hospitalization/prolonged hospitalization)
- whether it constitutes a serious adverse event (SAE)

All adverse events should be treated appropriately. Such treatment may include changes in study drug treatment including possible interruption or discontinuation, starting or stopping concomitant treatments, changes in the frequency or nature of assessments, hospitalization, or any other medically required intervention. Once an adverse event is detected, it should be followed until its resolution, and assessment should be made at each visit (or more frequently,

if necessary) of any changes in severity, the suspected relationship to the study drug, the interventions required to treat it, and the outcome.

Information about common side effects already known about the investigational drug can be found in the Investigators' Brochure. This information should be included in the patient informed consent and should be discussed with the patient during the study as needed.

3.4.3.2 Serious adverse events

Information about all serious adverse events will be collected and recorded. To ensure patient safety each serious adverse event must also be reported to Novartis within 24 hours of learning of its occurrence. A serious adverse event is an undesirable sign, symptom or medical condition which:

- is fatal or life-threatening
- results in persistent or significant disability/incapacity
- constitutes a congenital anomaly/birth defect
- is medically significant, i.e., defined as an event that jeopardizes the patient or may require medical or surgical intervention to prevent one of the outcomes listed above
- requires inpatient hospitalization or prolongation of existing hospitalization, unless hospitalization is for:
 - routine treatment or monitoring of the studied indication, not associated with any deterioration in condition (specify what this includes)
 - elective or pre-planned treatment for a pre-existing condition that is unrelated to the indication under study and has not worsened since the start of study drug
 - treatment on an emergency outpatient basis for an event not fulfilling any of the definitions of a SAE given above and not resulting in hospital admission
 - social reasons and respite care in the absence of any deterioration in the patient's general condition

3.4.4 Novartis and FDA instructions for rapid notification of serious adverse events

The principal investigator has the obligation to report all serious adverse events to the FDA, Novartis Pharmaceuticals Clinical Safety and Epidemiology Department (CS&E), and IRB.

Reporting to the FDA

The DF/HCC Overall Principal Investigator, as holder of the IND, will be responsible for all communication with the FDA. The DF/HCC Overall Principal Investigator will report to the FDA, regardless of the site of occurrence, any adverse event that is serious, unexpected and reasonably related (i.e., possible, probable, definite) to the study treatment.

Unexpected fatal or life-threatening experiences associated with the use of the study treatment will be reported to FDA as soon as possible but in no event later than 7 calendar days after initial receipt of the information.

All other serious unexpected experiences associated with the use of the study treatment will be reported to FDA as soon as possible but in no event later than 15 calendar days after initial receipt of the information.

All events meeting the criteria of an INDSR will be submitted to the appropriate division center via mail using Form FDA 3500A (Mandatory Reporting Form for investigational agents) in compliance with FDA reporting timelines. Forms are available at <http://www.fda.gov/medwatch/getforms.htm>.

Reporting to Novartis

All events must be reported, by [contact]), to Novartis Pharmaceuticals CS&E Department within 24 hours of learning of its occurrence. This includes serious, labeled (expected) and unlabeled (unexpected) adverse experiences. All deaths during treatment or within 30 days following completion of active protocol therapy must be reported within 5 working days.

Any serious adverse event occurring after the patient has provided informed consent and until 4 weeks after the patient has stopped study participation must be reported. This includes the period in which the study protocol interferes with the standard medical treatment given to a patient (e.g. treatment withdrawal during washout period, change in treatment to a fixed dose of concomitant medication).

Serious adverse events occurring more than 4 weeks after study discontinuation need only be reported if a relationship to the Novartis study drug (or therapy) is suspected.

For Comparator Drugs/Secondary Suspects (Concomitant Medications), all serious adverse experiences will be forwarded to the product manufacturer by the investigator.

3.4.5 IRB Instructions for notification of serious adverse events

For DF/HCC Sites:

The DFCI IRB SAE Reporting Form must be used to report SAEs experienced by DF/HCC participants enrolled in a DF/HCC study including any serious adverse events on DF/HCC led Multi-Center trials where the event occurs at a non-DF/HCC site. Full written SAE report must be submitted to OHRS as soon as possible, but no later than **10 working days** from notification of event. For DF/HCC participant centers, reports must be submitted via OHRS Submit, and the lead site must be notified prior to submission to OHRS.

The DFCI IRB requires the following events be reported:

- **Grade 2 (moderate) and Grade 3 (severe) Events** – Only events that are Unexpected and Possibly, Probably or Definitely Related/Associated with the Intervention.

- **ALL Grade 4 (life threatening or disabling) Events**
- **ALL Grade 5 (fatal) Events** – When subject is enrolled and actively participating in the trial OR when event occurs within 30 days of the last study intervention.

Follow Up SAE Reports (DF/HCC participating centers only):

When submitting follow up reports to previously reported SAEs, **attach a copy of the original report and any prior IRB determinations to the follow up report**. This gives the reviewer all the information required to conduct a thorough review and eliminates questions that might otherwise be raised.

For Non-DF/HCC Sites:

For institutions outside of DF/HCC, please report grade 2 or higher AEs considered unexpected and possibly, probably, or definitely related/associated with the intervention to DFCI Study Team ([name]: Principal Investigator) for reporting to the DFCI IRB. All outside institutions are also required to report events to their IRB per individual institutional guidelines.

3.4.5.1 Pregnancies

Any pregnancy that occurs during study participation should be reported. To ensure patient safety each pregnancy must also be reported to Novartis within 24 hours of learning of its occurrence. The pregnancy should be followed up to determine outcome, including spontaneous or voluntary termination, details of birth, and the presence or absence of any birth defects, congenital abnormalities or maternal and newborn complications.

4 Protocol amendments, or changes in study conduct

This protocol, the proposed informed consent and all forms of participant information related to the study (e.g., advertisements used to recruit participants) and any other necessary documents must be submitted, reviewed, and approved by a properly constituted IRB governing each study location.

Any changes made to the protocol must be submitted as amendments and must be approved by the IRB prior to implementation. Any changes in study conduct must be reported to the IRB. The Principal Investigator (or Protocol Chair) will disseminate protocol amendment information to all participating investigators.

All decisions of the IRB concerning the conduct of the study must be made in writing.

For Non-DF/HCC Sites:

For institutions outside of DF/HCC, any protocol or amendment changes need to be first approved by [name].

5 Correlative Studies

For correlative studies, patients will be asked for the permission to obtain and store either a tumor tissue block from a previous biopsy and/or undergo sequential biopsies.

If tumor tissue blocks are unavailable, then up to forty unstained slides should be obtained. These will be kept in the clinical research lab in a secure location.

They will be used for immune histochemistry (IHC) studies and possible analysis of genetic mutations in the future. IHC staining for the expression of AKT, PTEN, PI3K and others will be performed when funding becomes available. Analysis of mutations such as B-raf may also be performed depending on funding in the future. Patients may decide against participating but will be encouraged to give permission for using their tumor tissue.

6.1 Data collection

Investigators must record the information required by the protocol.

6.1.1 Data Safety

The DF/HCC Data and Safety Monitoring Committee (DSMC) will review and monitor toxicity and accrual data from this trial. The committee is composed of clinical specialists with experience in oncology and who have no direct relationship with the study. Information that raises any questions about participant safety will be addressed with the Principal Investigator and study team.

The DSMC will meet quarterly and/or more often if required to review toxicity and accrual data. Information to be provided to the committee may include: up-to-date participant accrual; current dose level information; DLT information; all grade 2 or higher unexpected adverse events that have been reported; summary of all deaths occurring within 30 days for Phase I or II protocols; for gene transfer protocols, summary of all deaths while being treated and during active follow-up; any response information; audit results, and a summary provided by the study team. Other information (e.g. scans, laboratory values) will be provided upon request.

7 Statistical methods

7.1 Statistical methods

This study is intended to provide initial efficacy data on RAD001 in patients with RAI refractory differentiated thyroid cancer and evidence for progressive disease. The design follows the two step method by Fleming et al³³. In the first step, 18 patients with differentiated thyroid cancer (excluding medullary and anaplastic thyroid cancer) and documented disease progression within 6 months will be enrolled. Then a PFS of 6 months or more will be required in at least two patients in order to proceed with the enrollment of 15 more patients for the study to complete its full accrual of the differentiated thyroid cancer part of the trial of 33 patients. The time interval of 6 months is chosen because documented disease progression within 6 months is a requirement for enrollment in this trial. Imaging studies will be obtained every 2 months and if no progression can be demonstrated at the 6 month time point while on therapy, anti-tumor activity is likely. If there is only one or no case alive and progression-free at 6 months in the first cohort, the drug combination will be considered ineffective and the trial will be terminated. If at least 2 subjects meet the criteria, the study will proceed to its full accrual of patients with differentiated thyroid cancer of 33 patients. Patients who drop out before the 6 month binary evaluation will be counted as failures. We will declare the trial a

success after observing 7 or more patients alive and progression-free at 6 months. The study will have $\alpha = 0.092$ and power = 0.970, assuming a 6 month PFS of 0.12 for the null and a PFS of 0.35 as the alternative hypothesis.

This trial will also include 2 separate exploratory cohorts for patients with medullary and anaplastic thyroid cancer to detect a possible signal in these rare diseases in which no established treatment alternatives exist. They are not included in the main analysis since there are important differences compared to differentiated thyroid cancer. Medullary thyroid cancer originates from parafollicular C-cells which are embryologically and molecularly distinct from the rest of the thyroid gland. Anaplastic thyroid cancer is also distinct from differentiated thyroid cancer with a high rate of distant metastasis and a poor prognosis. Ten patients with medullary thyroid cancer and seven patients with anaplastic thyroid cancer will be treated on this protocol and descriptive statistics will be used for analysis of these patient groups. If no signal is detected, no conclusions can be drawn. However, if there are a few responses (i.e. one or more), a case for a larger, multi-institutional effort to analyze this fully could be made.

Since we expect accrual of a relatively large number of medullary thyroid cancer cases based on the patient population that we see at DFCI, we wanted to make sure that the main group for which this trial is designed - papillary and follicular thyroid cancer- are sufficiently represented in the group of 33 patients of the primary analysis.

Thus the grand total of subjects on this trial will be 50.

We will use the Kaplan-Meier survival method and the Cox model to analyze PFS and the confidence intervals will be estimated.

For the categorical outcomes, logistic regression or chi-square test will be used. For the survival outcomes, the Kaplan-Meier method and the Cox regression model will be used.

8 References

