3.1 Overall study design

This is a non-randomized phase II study with RAD001 as first or second line treatment in patients who are either newly diagnosed with radioiodine refractory thyroid cancer or have progressed after chemotherapy with doxorubicine or a small molecule tyrosine kinase inhibitor such as Sorafenib and who have documented disease progression within 6 months.

Similar to prior studies in patients with thyroid cancer, all histologic thyroid cancer types will be included in this trial. While there may be differences in response to treatment between tumor types, this trial will provide an overview about responsiveness to therapy in this rare disease.

Our trial will follow a 2 step design according to Fleming's procedure³³. In the first step, 18 patients with differentiated thyroid cancer (excluding medullary or anaplastic thyroid cancer) and documented disease progression within 6 months will be enrolled. Then a PFS of 6 months or more will be required in at least two patients in order to proceed with the enrollment of 15 more patients for the study to complete its accrual of 33 patients. The time interval of 6 months is chosen because documented disease progression within 6 months is a

requirement for enrollment in this trial. Imaging studies will be obtained every 2 months and if no progression can be demonstrated at the 6 month time point while on therapy, anti-tumor activity is likely. If there is only one or no case of PFS of at least 6 months in the first cohort, the drug combination will be considered ineffective and the trial will be terminated.

In addition, two separate exploratory cohorts will be included in the trial but will not be part of the statistical analysis of the 2 step study. These cohorts include up to 10 patients with medullary thyroid cancer and up to 7 patients with anaplastic thyroid cancer, respectively. These cohorts will be evaluated by descriptive statistics and will provide an initial measure of efficacy in this disease in which no approved and effective treatment options exist. This brings the total number of subjects in this trial to 50.

The patients will be followed for a maximum duration of 24 months. Please see Section 3.4.1.3 for an outline of data that will be collected post 24 months for patient continuing on treatment without progression of disease.

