3.4 Visit schedule and assessments

3.4.1 Visit schedule

The visit schedule is outlined in Table 3.4a below.

General/safety assessments	Study entry (within 14 days of day 1 unless otherwise noted))	Day1 ²	At office visit every 4 weeks ¹	Every 8 weeks for max. 24 months ¹
Informed consent	X (within 28 days of day1)			
Medical history, height and vital signs	X		X	
Inclusion/exclusion criteria	X			
ECOG Performance status	X	X	X	
QOL questionnaire (EQ-5D)		X	X	
MTC-related symptoms questionnaire (MTC subjects only)		X	X	
Physical examination and weight	X	X	X	
ECG	X			
AE's and con-medications/treatments	X	X	X	
Laboratory assessments				
Pregnancy test for WOCBP (female subjects <50)	X			
Coagulation tests	X			
Hepatitis B tests (Hep B Core, Hep B Surf AB, Hep B Surf AG, HBV DNA) ³	X (within 30 days of Day 1)		X (only HBV DNA if positive at baseline)	
Hepatitis C test (HCV RNA PCR) ³	X (within 30 days of Day 1)			
Hematology and blood chemistry	X		X	
Urinalysis	X			
Calcitonin and CEA if elevated at baseline (only MTC subjects)	X		X (if elevated at baseline)	
Thyroglobulin and anti-thyroglobulin antibodies (only DTC subjects)	X		X (if elevated at baseline) ⁴	
Free T4 and TSH	X		X	
Radiological assessments				
CT/MRI neck, chest, abdomen ⁵	X (within 30 days of day 1)			X
Whole body bone scan (only MTC, FTC, HCTC subjects)	X (within 30 days of day 1)			
First dose of Rad001		X ²		
Rad001 dispensed/returned				X

- ¹+/- one week depending on appointment availability due to holidays or unforeseen events
- ²First dose of RAD001 may start the morning of Study Day 2.

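### Do the two wordings of the 6-month rule leave the trial's decision undefined for progression first seen on the third scan?

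*Combined protocol and SAP*

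**What the plan says.** The primary decision is a two-stage count in differentiated thyroid cancer: 18 patients, then 15 more if at least two succeed, with success declared at 7 or more of 33.

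- Section 3.1, stop rule: "If there is only one or no case of PFS of at least 6 months in the first cohort".
- Section 7.1, go rule: "Then a PFS of 6 months or more will be required in at least two patients in order to proceed".
- Section 7.1, stop rule: "If there is only one or no case alive and progression-free at 6 months in the first cohort".
- Section 7.1, final rule: "success after observing 7 or more patients alive and progression-free at 6 months".
- Section 7.1, drop-outs: "Patients who drop out before the 6 month binary evaluation will be counted as failures".

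Immediately after its stop rule, section 7.1 states the go decision a second time, as at least two subjects meeting the criteria just given. Sections 3.1 and 7.1 both explain the rule as a test of whether progression can be shown at the 6-month time point.

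On measurement, section 3.4.2 says "Progression-free survival will be measured based on the appearance of disease progression on imaging based on RECIST criteria". Table 3.4a schedules imaging "Every 8 weeks for max. 24 months", with a tolerance of plus or minus "one week depending on appointment availability due to holidays or unforeseen events". Section 3.4.1.2 also says every 8 weeks, with a 5-business-day window. Sections 3.1 and 7.1 and footnote 5 of the table say every 2 months. No section states the date from which PFS runs.

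**The concern.** PFS of at least six months and being progression-free at six months are not the same condition when progression is dated by a scan. If the third scan falls exactly at month 6 and is the first to show progression, PFS equals six months. The patient then meets the go rule near the start of 7.1 but counts against the stop rule a few lines later.

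The calendar does not obviously settle it. An 8-weekly third scan is due on day 168. Counted from enrolment, with the permitted delay to first dose and a late scan, it can fall after six calendar months.

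This count decides both whether stage 2 opens and whether the trial succeeds. If third-scan progressions were counted as successes throughout, while the null rate of 0.12 refers to patients clean at that scan, the type I error would be far above the stated value. In an open-label single-arm trial, that should not be left to a judgement made after the data are seen.

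**Working it through.** **1. The plan's own figures.** Inputs from section 7.1: 18 then 15 patients, continue with at least 2, success with at least 7 of 33, null 0.12, alternative 0.35.

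P(success) = Σ over x = 2 to 18 of P(Bin(18, p) = x) × P(Bin(15, p) ≥ 7 − x)

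- p = 0.12: 0.0915 (stated 0.092)
- p = 0.35: 0.9698 (stated 0.970)

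Both reproduce. P(stage 2 opens) at p = 0.12 is 1 − 0.3460 = 0.654.

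**2. Where each wording is used.** The looser wording is in the stop rule of 3.1 and the first go rule of 7.1, both stage 1. The stricter wording is in the stop rule of 7.1 and in the only statement of the final rule. The conflict in the text is therefore, at most, a looser stage-1 gate followed by the strict final count.

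**3. Effect of that conflict.** Let d be the share of patients first progressing on the third scan and counted as successes at the gate only. The documents do not give d, so k = 1, 2 and 4 extra patients per 33 are assumed (d = k/33). For x strict successes in stage 1, the gate opens if x plus the extras reach 2. Each strict failure is an extra with probability d/(1 − 0.12). The final count uses strict successes only.

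| k per 33 (assumed) | P(stage 2 opens), null | Alpha |
|---|---|---|
| 0 | 0.654 | 0.0915 |
| 1 | 0.777 | 0.0921 |
| 2 | 0.862 | 0.0925 |
| 4 | 0.953 | 0.0929 |
| gate always open | 1 | 0.0930 |

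The last row needs no assumption about d: it is P(Bin(33, 0.12) ≥ 7) and bounds alpha. Alpha barely moves because a trial with 0 or 1 strict successes in 18 would need at least 6 more among 15. The added probability is 0.1002 × 0.00096 + 0.2458 × 0.00569 = 0.0015. The same bound for power is P(Bin(33, 0.35) ≥ 7) = 0.9717.

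The cost is in patients. Expected enrolment under the null is 18 + 15 × 0.654 = 27.8, and 18 + 15 × 0.777 = 29.7 with k = 1.

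**4. Whether the calendar separates the wordings.** Six months is 182.6 days. An 8-weekly third scan is due on day 3 × 56 = 168, or 161 to 175 with one week either side. Counted from first dose, progression on it comes before six months and fails both wordings. Counted from enrolment, 10 business days (about 14 days) may be added, giving day 161 to 189. To reach day 183 the dosing delay and scan slippage together must use 183 − 168 = 15 of the possible 14 + 7 = 21 days. If scans are instead taken at exact 2-month intervals, the third is at month 6 and the wordings do part. The second statement of the go rule in 7.1 and the stated rationale then make that patient a failure.

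**The case for a change.** The strongest case for acting is that the whole decision rests on this count, the margin is one patient, and the remedy is only wording. Under the null the trial passes stage 1 and finishes with exactly 6 successes with probability 0.099. If the looser reading governed the final count as well, one, two or four extra null successes per 33 would raise alpha to 0.22, 0.38 or 0.71. The rationale sentence that points to failure names no scan, week or window.

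The arithmetic is right, but it describes a rule the plan does not contain: the final count is worded once, and strictly. What stands is smaller. The deciding scan is not numbered, the PFS start date is unstated, two months and eight weeks are used as one interval, and one stage-1 phrase is loose.

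Two related worries carry little weight. Five business days is one calendar week, so the two windows nearly coincide, although section 3.4.1.2 gives no direction. A patient clean on the third scan and lost afterwards has already had the binary evaluation, and the drop-out rule fails only those who leave before it.

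**Conclusion.** No change to the plan follows. The natural reading is that progression on the third scheduled scan, nominally month 6, is a failure at both stages. Alpha 0.0915 and power 0.9698 then stand, provided 0.12 and 0.35 are rates at that scan. Even if the loose stage-1 phrase were taken literally, alpha is bounded by 0.0930 and power by 0.9717, whatever the share of patients progressing on that scan. The only material effect would be opening stage 2 more often for an inactive drug, from 0.65 to 0.78 with one extra patient per 33, a number the documents do not supply. The unnumbered scan and unstated PFS start date are details an analyst fills in the evident way; doing so changes no threshold, stated figure or conclusion.

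### Is declaring success at 7 of 33, with a type I error of 9.2% and 97% power, a flaw when 8 of 33 would give 3.8% and 93%?

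*Combined protocol and SAP*

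**What the plan says.** Section 7.1 names its method: "The design follows the two step method by Fleming et al". Eighteen patients are enrolled first. At least two must reach 6 months without progression "in order to proceed with the enrollment of 15 more patients", for 33 in all. The stopping side reads "If there is only one or no case alive and progression-free at 6 months in the first cohort", in which case the trial ends. At full accrual the trial is declared a "success after observing 7 or more patients alive and progression-free at 6 months". Patients who leave before 6 months count as failures, so the denominator stays at 33.

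The operating characteristics are given outright: "The study will have $\alpha = 0.092$ and power = 0.970", for a 6-month rate of 0.12 under the null and 0.35 under the alternative. No target for either error is stated, and no reason is given for choosing 7. The section also says that Kaplan-Meier and Cox methods will be used to "analyze PFS and the confidence intervals will be estimated".

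**The concern.** The two errors look out of balance. The plan accepts a false-positive risk above 9% while holding the false-negative risk at 3%. With the same 33 patients, raising the cut-off by one patient brings the type I error below 0.05 and leaves power above 0.90 at the design alternative.

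Three further observations seem to point the same way. At 7 of 33 (21.2%) the exact 95% confidence interval includes the null of 0.12, so the trial could claim success beside an interval that contains the rate it claims to exceed. Section 7.1 gives no source for 0.12, and a higher true null inflates the false-positive risk. And under the null the first-stage rule lets the trial continue about two times in three.

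Section 2 says that promising activity would be the basis for larger studies. If the cut-off were truly too lenient, a false success would carry patients with a rare disease into a larger trial of an inactive drug.

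**Working it through.** **Inputs (section 7.1).** First stage n1 = 18, continue if X1 ≥ 2; second stage n2 = 15; success if the total is at least r = 7; p0 = 0.12, p1 = 0.35. Success is declared only on a high count, so the type I error is one-sided.

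**Formula.** P(success | p) = Σ over x = 2 to 18 of P(X1 = x | 18, p) × P(X2 ≥ r − x | 15, p).

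**The plan's own figures.** With r = 7 the sum is 0.0915 at p0 and 0.9698 at p1. These round to the stated 0.092 and 0.970.

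**Other cut-offs, same 18 + 15 patients and same first-stage rule.**

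| Cut-off | Type I error | Power at 0.35 | Type II error |
|---|---|---|---|
| 7 | 0.0915 | 0.9698 | 0.0302 |
| 8 | 0.0376 | 0.9331 | 0.0669 |
| 9 | 0.0134 | 0.8679 | 0.1321 |

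From 7 to 8 the type I error is multiplied by 0.0376 / 0.0915 = 0.41 and the type II error by 0.0669 / 0.0302 = 2.2. One is more than halved and the other more than doubled.

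**What the named method gives.** Fleming's final cut-off is floor(33 × 0.12 + z × √(33 × 0.12 × 0.88)) + 1. Here 33 × 0.12 = 3.96 and √3.4848 = 1.867.
- One-sided 0.10 (z = 1.2816): 3.96 + 2.39 = 6.35, so the cut-off is 7.
- One-sided 0.05 (z = 1.6449): 3.96 + 3.07 = 7.03, so the cut-off is 8.

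The plan's 7 is therefore the method applied at one-sided 0.10, and the exact error of 0.0915 lies within that level.

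**Power below the design alternative.** The 0.933 for cut-off 8 holds only at a true rate of 0.35. The documents do not say whether 0.35 already allows for drop-outs. The table assumes that it does not, and that the given share of would-be successes is lost before 6 months; the row at 0.30 is simply an assumed lower true rate.

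| Effective rate | Cut-off 7 | Cut-off 8 |
|---|---|---|
| 0.315 (10% lost: 0.35 × 0.90) | 0.929 | 0.861 |
| 0.30 (assumed) | 0.902 | 0.816 |
| 0.2975 (15% lost: 0.35 × 0.85) | 0.897 | 0.808 |
| 0.28 (20% lost: 0.35 × 0.80) | 0.853 | 0.743 |

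**Confidence limits (exact, Clopper-Pearson).**

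| Result | One-sided 90% lower | One-sided 95% lower | Two-sided 95% lower |
|---|---|---|---|
| 7/33 | 0.122 | 0.104 | 0.090 |
| 8/33 | 0.147 | 0.127 | 0.111 |

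At the one-sided 90% level, which is close to the design's own, the bound at 7/33 lies above 0.12. The 95% bounds fall below 0.12 because the type I error was set near 0.09, so they restate that choice and add no evidence against it. The two-sided 95% limit at 8/33 is also below 0.12, so the stricter cut-off would not cure that mismatch.

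**First stage.** Under the null, P(X1 ≤ 1) = 0.100 + 0.246 = 0.346, so the trial continues with probability 0.654 and the expected size is 18 + 15 × 0.654 = 27.8. Requiring 3 of 18 would stop 0.631 of null trials early, with expected size 18 + 15 × 0.369 = 23.5. It would also raise the chance of stopping an active drug (0.35) at the first look from 0.005 to 0.024. Combined with cut-off 8, power would be 0.925 at a true rate of 0.35 and 0.795 at 0.2975.

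**The case for a change.** The strongest case for 8 is made at the plan's own design values. There it is the only cut-off with a type I error below 0.05 and power above 0.90, and it needs no more patients. It also gives more protection if the null is too low: at an assumed true null of 0.15, false success is 0.214 with cut-off 7 and 0.110 with cut-off 8. The trial has no concurrent control to reveal a misjudged null, and section 7.1 does not say where 0.12 comes from or why 7 was preferred.

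All of those figures are correct, and another statistician could reasonably have chosen 8. They show a preference and not a defect. The 0.05 line is not in the documents. The missing source for 0.12 is a separate matter that a stricter cut-off would not settle, since 11% false success would remain at 0.15. Robustness also has to be looked at from both ends: a higher null favours 8, and a lower true effect or early drop-out favours 7.

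Nor would the change be free. Appendix D, section 5.4, counts a change to the statistical section as a major amendment that needs full ethics board approval. In an open-label single-arm trial, moving the success threshold after outcomes are known would raise a problem of its own; the documents do not give the accrual status.

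**Conclusion.** The concern does not hold. The stated 0.092 and 0.970 are correct for the stated rule, the cut-off is the one Fleming's formula gives at one-sided 0.10, and no rule or target in the documents is missed. Going to 8 would lower the type I error by 5.4 percentage points (0.0915 − 0.0376) and power by 3.7 points (0.9698 − 0.9331) at a true rate of 0.35. At an assumed 0.30 the loss of power grows to 8.6 points (0.902 − 0.816).

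Which error to favour is a judgement. Section 7.1 describes the aim as initial efficacy data, section 1.1.3.3 calls this the first study of the drug in thyroid cancer, and section 2 makes further study the consequence of a success. In that setting, giving priority to not missing an active drug is legitimate, and the price is stated openly. The 2-of-18 first-stage rule reflects the same priority. This conclusion takes 0.12 as the null; whether that rate is well supported is a different question.
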